## 14.0 WITHDRAWAL OF SUBJECTS

Early withdrawal of study subjects. As stated on the Informed Consent, all subjects reserve the right to withdraw from the clinical investigation at any time. The PI for any of the following reasons may discontinue subjects from the study:

- Subject is found to have entered the study in violation of the protocol.
- Subject withdraws consent to participate in the study.
- Subject is unable to tolerate the pre-treatment MRI.
- Subject is noncompliant with procedures set forth in the protocol.
- Subject experiences an Adverse Event that warrants withdrawal from the study.
- It is in the PI's opinion that it is not in the subject's best interest to continue.

- Subject displays other abnormal laboratory, medical or clinical findings for which clinical intervention should take precedence over study participation including:
  - a) Development of mania/hypomania
  - b) Generalized seizure
  - c) Inpatient hospitalization
  - d) Unable to complete desired treatment in the designated time frame

If a participant is lost to follow up, three documented attempts will be made to contact the participant.

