**Sessions 3-5: rTMS (2 – 3 hours).** A MagVenture MagPro TMS System will be utilized. All participants will receive open-label treatment for approximately eight, 3-minute sessions of intermittent theta burst rTMS on each of three days within an eight-day span. A single session=600 pulses at 120% rMT, iTBS triplets at 50 Hz for 2 s and repeated every 10 s for a total of 190 s to left dlPFC. Total pulses=14,400. To enable adherence and retention, the days do not need to be contiguous. Same day sessions will be separated by 10-15 minutes, but more accounting for participant comfort. After each day of treatment, participants will be asked to complete an rTMS acceptability questionnaire. During treatment breaks participants will complete Momentary Assessment of TMS and 10-15 minutes of Brain HQ exercises between each session and will also have the option of completing tasks at home on intervening days during the treatment schedule. At the end of the final treatment session, participants will be asked to rate the exercises based on difficulty and enjoyment.

**Session 6: In-person Post-treatment Neurocognitive/Neuropsychiatric Assessment (2 - 3 hours).** Within one week following treatment, participants will repeat the pre-treatment neuropsychiatric and neurocognitive assessment for assessment of pre/post treatment changes.

**Session 7: Post-treatment MRI Scans (1 - 2 hours).** Within one week following treatment, participants will repeat the pre-treatment MRI scans for assessment of pre/post treatment changes.

**Session 8: 1 – 3 weeks post-treatment completion.** During the intervening weeks after Sessions 6/7 and before Session 9, the participants will be asked to remotely complete surveys using REDCap. Participants will also be provided with a research account for BrainHQ and asked to engage in at least 20 minutes of brain exercises daily until Session 9.

**Session 9: 4 weeks post-treatment completion.** Participants will again be asked to complete surveys using REDCap. Participants will also be asked to complete the MoCA remotely, as well as acceptability/satisfaction questionnaires regarding the rTMS and BrainHQ interventions.

**Participant Compensation.** Participants will be compensated as follows:

Consent & Session 1:	\$40 for screening and pre-treatment assessments
Session 2:	\$50 for the pre-treatment MRI
Sessions 3 to 5:	\$120 for rTMS treatment (i.e. \$40/day)
Sessions 6 and 7:	\$100 for post-treatment assessments and MRI

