Consent and HIPAA forms will be kept on file for 6 years. Contact information is kept on file for 6 years if the participant consents to allowing their information to remain active in our files, or the contact information is destroyed immediately after the study is completed if participants chose that option on the consent form. Although individual-subject analyses may be written up in publications, the individual subjects producing that data will never be identified by name or initials, or any other identifying information.

*Other protections against risk.* In designing this trial, the research team sought to maximize data collection within the overall priority of maintaining participant comfort and safety. As was discovered in the pilot study by George and colleagues, the proposed design is feasible, does not impose unreasonable expectations of time or effort, or expose patients to risks or limit them from the best available care. In the very unlikely event that a subject endorses transient alcohol or substance abuse during the course of this study, the coordinator will confer with a physician co-investigator prior to proceeding with any treatment.

*Adverse Events & Trial Safety.* Potential conflicts of interest will be reported using the NIH rules for disclosure. Adverse Events (AEs)/Serious Adverse Events (SAEs) occurring during the course of the project will be collected, documented, and reported in accordance with protocol and IRB reporting requirements. All research staff involved with adverse event reporting will receive general and protocol specific AE/SAE training including identification, assessment and evaluation, and documentation and reporting. Any potential adverse events will be identified during the course of the study from participant self-report and administration of the visit assessments and procedures. Research staff will identify adverse events and obtain all available information to assess severity, seriousness, study relatedness, expectedness, outcome and the need for change or discontinuation in the study intervention.

An Adverse Event (AE) is defined as any unwanted change, physically, psychologically or behaviorally, that occurs in a study participant during the course of the trial is an adverse event. A Serious Adverse Event (SAE) is defined as an adverse event that has one of the following outcomes:

- Results in death,
- Is life-threatening,

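### Section 14 provides only for exit from the study, and nothing visible keeps participants who stop after iTBS in for the only post-treatment MRI and full cognitive battery

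*Combined protocol and SAP*

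**What the plan says.** Section 14.0 gives participants the right to withdraw from the investigation and then states: "The PI for any of the following reasons may discontinue subjects from the study". This exit is discretionary, and it is an exit from the study. One listed reason is "Subject experiences an Adverse Event that warrants withdrawal from the study". Another is a group of findings "for which clinical intervention should take precedence over study participation", with four sub-items: mania or hypomania, generalized seizure, inpatient hospitalization, and "Unable to complete desired treatment in the designated time frame".

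The section's only follow-up step is this: "If a participant is lost to follow up, three documented attempts will be made to contact the participant".

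Two other places bear on people who stop iTBS early:

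- Section 13.0, in the paragraph on adverse events and trial safety, has staff assess "the need for change or discontinuation in the study intervention" when an event occurs. So stopping the intervention alone is contemplated.
- Section 10.0 says for Session 6: "Within one week following treatment, participants will repeat the pre-treatment neuropsychiatric and neurocognitive assessment for assessment of pre/post treatment changes". For Session 7 it says: "Within one week following treatment, participants will repeat the pre-treatment MRI scans for assessment of pre/post treatment changes". Neither sentence is limited to people who completed iTBS.

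Section 4.0 lists three primary outcomes for Aim 1: structural brain change, neurocognitive change and adverse events. For Aim 1, the analysis text in Section 12.0 provides for scan review and a summary of adverse events. It names no denominator.

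**The concern.** Aim 1 is the safety aim, and its hypotheses in Section 1.0 are absolute: no clinically significant structural change, no cognitive decrement, no significant adverse events. Against claims of that kind, a few unmeasured people can matter. The reasons for exit in Section 14.0 include the events a safety study most needs to follow; Section 15.0 names seizure as the primary safety concern.

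If a participant has such an event after stimulation and is discontinued from the study, the event is recorded, but the scan and the cognitive battery that would show what followed are not scheduled. The structural and cognitive results would then describe mainly those who got through treatment, and could look safer than the experience of everyone treated. Ad hoc decisions about who stays in to be scanned would be a source of selection in themselves.

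**Working it through.** The central question is one of reading, so the passages are set side by side first. A short illustration of scale follows.

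**Step 1. Where the outcomes are measured after treatment** (schedule table and session descriptions, Section 10.0).

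| Measure | Scheduled post-treatment occasions | Obtained if discontinued from the study before Session 6 |
|---|---|---|
| Structural MRI | 1 (Session 7) | 0 of 1 |
| NIH Toolbox and NINDS-CSN battery | 1 (Session 6) | 0 of 1 |
| MoCA | 2 (Sessions 6 and 9) | 0 of 2 |

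No later visit can recover the MRI or the full battery.

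**Step 2. Does any visible text keep a treated early stopper in for those visits?**

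- *Section 14.0, three contact attempts.* These are for people lost to follow-up, not for people the PI discontinues. The one place that defines lost to follow-up, the confidentiality text in Section 13.0, ties it to missing intake within a month of screening, which is before treatment.
- *Section 13.0, discontinuing the intervention.* This is something to assess about an event. No follow-up visit is attached.
- *Section 13.0, monitoring of active adverse events.* It covers unexpected events, and its purpose is to decide whether treatment is needed. No MRI or battery is included.
- *Section 15.0, daily symptom checks and weekly physician contact.* The weekly contact covers mood, functioning and safety during treatment and the one-month involvement. Again there is no MRI or battery.
- *Section 10.0, Sessions 6 and 7.* The wording can cover an early stopper who remains enrolled. It does not reach someone already discontinued under Section 14.0.

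None of the five does so.

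**Step 3. Which Aim 1 outcomes are exposed?** Structural change and neurocognitive change, 2 of 3. The third is largely protected: the triggering event is itself recorded, active unexpected events are monitored, and deaths are reportable to 30 days after termination.

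**Step 4. Scale.** The plan enrolls 40 for 30 completers (Section 6.0). No attrition rate is given. An attrition of 25% reproduces the figure: 30 / (1 − 0.25) = 40. The retention target of over 80% in Section 1.0 would give 30 / 0.80 = 37.5, or 38. Neither figure says how many people will be treated and then go unscanned.

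As an illustration only, assume all 40 are treated and m of them lack the post-treatment MRI, with m anywhere from 0 to 10. Suppose no structural change is seen in the 40 − m who are scanned.

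- Exact one-sided 95% upper limit from those scanned: 1 − 0.05^(1/(40 − m)).
- Highest possible proportion with a change among all treated: m/40.

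| m (assumed) | Scanned | Upper limit if unscanned resemble scanned | Highest possible proportion among all 40 |
|---|---|---|---|
| 0 | 40 | 7.2% | 0/40 = 0% |
| 8 | 32 | 8.9% | 8/40 = 20% |
| 10 | 30 | 9.5% | 10/40 = 25% |

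The third column changes little with m, because it assumes the missing resemble the measured. The fourth column shows what that assumption carries.

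**The case against.** The strongest reply is that the documents are silent on early stoppers rather than directing their removal. The PI's power is discretionary. The adverse-event reason is limited to events that warrant leaving the study, which leaves room for events that end iTBS only. A section on withdrawal naturally describes withdrawals, and Section 10.0 can be read to bring early stoppers back. All of this stands. It shows that retention is permitted; it does not show that anything requires it.

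Four stronger readings are tempting but are not supported:

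- *That Section 14.0 removes anyone who misses any part of the 24 planned sessions.* The sub-item on unfinished treatment sits under the clause about clinical intervention taking precedence, so it may not be a free-standing rule. Section 10.0 also describes the daily number of sessions as approximate.
- *That bias is established.* Some exits, such as noncompliance, need have nothing to do with brain or cognitive change. A participant removed for a seizure still counts in the adverse-event outcome, so the overall Aim 1 conclusion need not be distorted.
- *That 10 of 40 will lack the data.* Section 12.0 defines retention as completing every session. A non-completer may have missed only Session 8 or 9 and still have been scanned, or may have left before any stimulation.
- *That the loss would go unseen.* Retention is an Aim 2 primary outcome, participant status goes into quarterly reports, and the DSMB reviews retention. These reveal attrition, but they give Aim 1 no denominator and do not say who lacks a scan.

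Mixed models are not an answer either. Section 12.0 assigns them to the exploratory aims, and they would not remove bias from harm-related missingness without strong assumptions.

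**Conclusion.** The point holds in limited form. Section 14.0 provides only for discontinuation from the study, at the PI's discretion, and no visible passage keeps a participant who stops after iTBS in for the single post-treatment MRI or the single post-treatment full battery. People who did badly on iTBS can therefore be missing from two of the three Aim 1 primary safety outcomes, and this could bias those two toward safety. The adverse-event outcome is largely protected.

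The number affected cannot be derived from the documents, and the illustration above rests on an assumed range. The conclusion also depends on the visible text: Section 14.0 refers to the informed consent form, which could not be checked and might contain a relevant commitment. The matter goes beyond tidying of wording, because the exit rule as written can selectively remove the most informative participants and the remedy is cheap.

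**What to change.** (a) In Section 14.0, distinguish stopping iTBS from leaving the study. Ask everyone who received any iTBS to attend the already planned Sessions 6 and 7 and the remote follow-up, unless consent is withdrawn or attendance is medically unsafe. Reconcile Section 14.0 with the Session 6 and 7 text in Section 10.0 and with the adverse-event text in Section 13.0. When treatment stops remains for the sponsor to decide; nothing here bears on that.

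(b) In Section 12.0, report the Aim 1 outcomes with all participants who received any iTBS as the denominator. State how many lack the post-treatment MRI or testing, and why.

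The cost is a few sentences of protocol text and a small scheduling effort, using assessments already planned for every participant. Some who stop will decline to return, so the missing counts under (b) are needed even with (a) in place.

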## 15.0 RISKS TO SUBJECTS

Challenges will include patient tolerability to TMS, the MRI scanner, and the study clinical and neurocognitive assessments. The primary safety concern, the same as that for conventional once-daily rTMS, is risk of seizure. However, all reported TMS-induced seizures during conventional or accelerated protocols have been self-limiting, and NONE required further intervention to stop the seizure; no post-seizure sequelae or recurrent seizures developed. Extensive precautions with regard to suicidal ideation/homicidal ideation risk will be followed.

Due to the novel nature of the proposed study, the following table is included to provide a representative range of the stimulation parameters and populations examined with accelerated rTMS. The dosing range of these studies covers the range proposed in this study. In these as well as other accelerated rTMS studies, the authors have demonstrated the safety, feasibility and acceptability of accelerated, high-dose studies of rTMS in neurologically intact samples. Of pertinence to the issue of safety as well as the conceptual model proposed here, Holtzheimer et al. showed reliably enhanced neuropsychological performance on the Repeatable Battery for the Assessment of Neuropsychological Status (RBANS) from baseline to six weeks after an accelerated, high-dose rTMS protocol in patients with major depression. Furthermore, Baeken et al. as well as Herremans et al. and Williams et al. additionally collected structural and functional imaging and demonstrated no adverse changes pre- to post-accelerated rTMS. Taken together, these studies demonstrate that the potential risks of accelerated rTMS are likely similar to conventional once-daily rTMS.

### Representative accelerated rTMS studies for neuropsychiatric conditions.

Study	Total Pulses	Days	Total # Sessions	Stimulation Intensity	Disorder	Frequency	N
Holtzheimer et al. 	15,000	2	15	100%	Major Depression	10 Hz; 5s train, 25s ITI	14
Baeken et al. 	31,200	4	20	110%	Major Depression	20 Hz; 1.9s train; 12s ITI	15
Herremans et al. 	31,200	3	15	110%	Alcohol Use Disorder	20 Hz; 1.9s train; 12s ITI	19
Desmyter et al. 	32,400	4	20	110%	Major Depression	54 bursts of three; 2s train; 8s ITI s	50
Duprat et al. 	32,400	4	20	110%	Major Depression	54 bursts of three; 2s train; 8s ITI s	50
George et al. 	54,000	3	9	120%	Suicidal ideation	10 Hz;	41

McGirr et al. 	60,000	10	20	120%	Major Depression	10 Hz; 5s train, 25s ITI	27
Modirrousta et al. 	90,000	3	30	110%	Major Depression	10 Hz; 5s train, 25s ITI	18
Williams et al. 	90,000	5	10	90%	Major Depression	54 bursts of three; 2s train; 10s ITI	7
Schulze et al. 	120,000-180,000	10-15	20-30	120%	Major Depression	20 Hz; 2.5s train; 10s ITI	65

Weighing potential risks related to TMS. Based on previous clinical applications of left prefrontal rTMS in depression and in various other psychiatric disorders, as well as risks published by researchers and communicated experiences, it is hypothesized that left prefrontal rTMS is likely to be effective in reducing psychosocial impairment. This study is an important necessary step to characterize the safety, feasibility, and tolerability of the proposed neurocognition enhancing effect.

Potential worsening of neuropsychiatric symptoms with TMS. Several studies have thus far demonstrated the feasibility of using rTMS in depression without any alarming indicators of exacerbation of symptoms. The research team will work closely with patients to familiarize them with the nature of this experimental setup. All staff will also be trained to be alert to any worsening of neuropsychiatric symptoms and/or psychosocial impairment. Bipolar patients have at times shown hypomanic or manic switches in the course of once-daily rTMS, as such patients with bipolar type I will be excluded. Additionally, all patients will be assessed throughout each day for worsening symptoms. Participants will similarly be queried for worsening suicidal ideation/intent. Drs. [name] or [name] will additionally assess each patient once per week in-person or via telephone during rTMS treatment and the one month study involvement to assess mood, functioning, and safety.

Potential risk of a seizure with TMS. There is a risk that TMS can cause a seizure; but it is rare. The risk of seizure induction is related to the intensity, duration, frequency and rest interval of stimulation. Following the adoption and widespread use of the safety guidelines from a National Institute of Neurological Disorders and Stroke (NINDS) workshop on TMS, only 20 seizures have been reported since 1997, and they usually involved parameters of "higher settings" than the "safe range". To our knowledge, stimulation with the parameters and settings proposed in this study should not cause seizures. Each subject's stimulus intensity is determined by his or her motor threshold and will be carefully calculated before beginning treatment. In this study participants will receive rTMS to the prefrontal cortex, a region far less prone to seizure. Nonetheless, we will watch participants closely for any signs of seizure throughout all procedures. Additionally, our study patients will be free from using known stimulants and medications that are known to increase the risk of seizure (e.g., theophylline).

Other potential effects of TMS on brain tissue. TMS is thought to be safe, with no brain damage, despite extensive use in humans and other animals. [name] and colleagues have recently completed a case report of a maintenance treatment of rTMS for depression over a year, where a depressed patient received a total of  $[(16,000 \times 2 \text{ trials}) + (8,000 \times 12 \text{ trials})] = 32,000 + 96,000 = 128,000$  stimuli over a year period. The patient's MRI showed no structural changes at the end from baseline. The patient experienced no seizures and had tolerated the procedure equally throughout the successive trials. [name] and colleagues have also reported a safety study looking at the MRI scans before and after 2 weeks of daily left prefrontal rTMS for depression.

Specifically, no structural changes were found in the left prefrontal lobe of patients who received active rTMS compared to placebo. More specific to the current study, Baeken et al. as well as Herremans et al. and Williams et al. additionally collected structural and functional imaging and demonstrated no adverse changes pre- to post-accelerated rTMS. Taken together, these studies demonstrate that the potential risks of accelerated rTMS are likely similar to conventional once-daily rTMS.

Potential changes in cognitive function. There have been no reports of deleterious changes (more than a minute) in cognitive function (memory, attention, etc.) in rTMS studies. Safety studies specifically looking for these changes did not find any effects of rTMS. Holtzheimer et al. showed reliably enhanced neuropsychological test performance from baseline to six weeks after an accelerated, high-dose rTMS protocol in patients with major depression. Similar effects have been observed in Alzheimer's Disease and schizophrenia. This study will assess for potential changes in cognitive function with pre- and post-treatment cognitive batteries designed to look for potential TMS effects, if they exist.

Potential hearing loss. The discharge of the rTMS coil generates a high-energy click that may cause cochlear damage. Humans exposed to rTMS have shown temporary increases in auditory threshold (especially at high frequencies) lasting at least 5 minutes and less than 4 hours. Foam earplugs can protect against these changes and will be worn by the patients and researchers present during TMS sessions. Due to high dosage delivery in this proposal, participants will be instructed to ensure proper fit of earplugs prior to each session.

Risk of facial twitching and skin irritation. The TMS coil can cause facial twitching, skin irritation, or both, which can be acutely unpleasant. This typically often reduces over the course of treatment. Additionally, all patients will have a foam insert placed between the coil and their scalp for comfort and this typically reduces this discomfort. Furthermore, facial twitching and skin irritation are typically only acute and subside with the end of stimulation.

Risk of a first-degree burn. The TMS coil can heat up during use. The machine used in this study has two major protective engineering features: (1) an external heat monitor that will shut down the system if the coil gets too warm; and (2) a liquid-coiled coil design that keeps the coil much cooler than previous models. Additionally, all patients will have a foam insert placed between the coil and their scalp for comfort and also to act as additional thermal protection. The TMS treater will periodically monitor coil temperature during each treatment.

Potential risks related to delaying other psychotropic treatments. The investigators are sensitive to the ethical concerns of withholding changes in antidepressant medication from depressed patients or withdrawing them from antidepressants in an acute crisis due to their participation in a clinical trial. Thus in this trial, patients are allowed to stay on medications and to have their physicians adjust doses or even start new medications. The rationale is that the effects of medication changes or new medications are rarely visible within the 'trial' of acute TMS. Thus, ethically treatment as usual will be allowed and also address our hypothesis, without subjecting patients to slower medication adjustments by participating in the trial.

MRI risks. Exposure to magnetic field strengths used in the present study is not shown to be a significant health risk. Risks to an unborn fetus from exposure to the MRI field strength used in the proposed research (3 Tesla) are unknown. Participants will be asked to lie still and awake for

50-60 minutes in the scanner and this can occasionally result in soreness, stiff back, etc. Participants will be queried approximately every 10 minutes about their comfort. The main risk associated with MR imaging is the possibility of introducing metal to the magnet or its close proximity. Participants are thoroughly screened to prevent metal being brought into the MR environment. Other potential hazards of MRI scanning include: collision hazards, noise, neurostimulation at rapid sampling rates (i.e., short TRs), body temperature changes, helium, and nitrogen hazards. The MRI facility is tested regularly by internal and external safety monitoring teams. These risks are minimal, and the facility is run within FDA guidelines. All investigators and research assistants running participants in the Center for Biomedical Imaging are thoroughly trained in MR safety as a requirement to run scans.

**Confidentiality Risks.** There is a risk of a loss of confidentiality of personal information as a result of participation in any study. This is why all study records and audio recordings will be placed in a locked, secure, limited access location. Participation in the study and the information provided will be treated as confidential. The information we collect will contain a code number and not a name to protect confidentiality. Codes linking numbers and names will be kept in a locked secure location and will not be accessible to anyone outside the research team. Despite these efforts to maintain subjects' anonymity and confidentiality, there is always some minimal risk of people other than the study investigators gaining access to health information. Every effort will be made to ensure that health information will be collected and stored in a manner that ensures the highest level of protection of confidentiality.

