### Exclusion Criteria:

- i. Dementia diagnosis per DSM-5 or NIA-AA criteria.
- ii. Daily/weekly use of anticholinergics, neuroleptics, sedatives, or bupropion. Stimulant use may be allowed pending investigator review. Cholinesterase inhibitors, NMDA receptor

antagonists, and antidepressants are allowed if on a stable regimen of four weeks prior to enrollment.

- iii. History of significant or unstable condition/s that may impact cognition such as significant cardiac, cerebrovascular, or metabolic disease, severe mental illness (e.g. bipolar disorder, psychoses), alcohol or substance use disorder, developmental disorder, or other neurologic disease (e.g. severe brain injury, seizures).
- iv. MRI and TMS contraindications (e.g., implants, claustrophobia, conditions/treatments that lower seizure threshold, taking medications that have short half-lives, no quantifiable motor threshold, active substance use disorder, bipolar disorder).
- v. Is enrolled in a clinical trial and/or has received an investigational medication within the last 30 days.

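### Section 15.0 lets physicians start new drugs during the trial without excepting those that lower seizure threshold, and no named treatment-day step checks for a medication change

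*Combined protocol and SAP*

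**What the plan says.** Four parts of the combined protocol and SAP bear on this.

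- **Section 15.0, paragraph on delaying other psychotropic treatments.** During the trial "patients are allowed to stay on medications and to have their physicians adjust doses or even start new medications". The stated motive is the "ethical concerns of withholding changes in antidepressant medication from depressed patients". The stated justification is that "effects of medication changes or new medications are rarely visible within the" period of acute TMS. Seizure is not mentioned.
- **Section 15.0, paragraph on the risk of a seizure.** Here the protocol promises that "our study patients will be free from using known stimulants and medications that are known to increase the risk of seizure", with theophylline as its example. The opening of section 15.0 names seizure as the primary safety concern.
- **Section 5.0, exclusion criteria.** Criterion ii excludes "Daily/weekly use of anticholinergics, neuroleptics, sedatives, or bupropion" and requires permitted antidepressants to have been stable for four weeks before enrollment. Criterion iv excludes "conditions/treatments that lower seizure threshold" as a TMS contraindication.
- **Section 10.0, schedule and session descriptions.** The Keel TMS Safety Screen is listed at Sessions 0 and 1 only. Sessions 3 to 5 list an adverse-events questionnaire, the Momentary Assessment of TMS, an acceptability questionnaire, stimulation at 120% of resting motor threshold, and the computerized exercises.

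**The concern.** One paragraph of section 15.0 gives an unqualified assurance about seizure-promoting drugs. Another gives an unqualified permission that can defeat it. The permission is exercised by the participant's own physician, who is outside the study team, so the team learns of a new drug only if it asks or is told.

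The reason given for the permission does not reach the safety question. That a new drug rarely shows a visible effect over a few days of treatment is an argument about interpreting outcomes. It says nothing about whether stimulation is safe once the drug is on board.

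At stake is the hazard that the protocol itself ranks first. A participant eligible at entry could start a drug that would have excluded them and be stimulated without any named prompt to find this out.

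**Working it through.** No formula applies and the plan gives no figure to reproduce. The check sets the texts side by side.

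1. **Scope of the permission.** It covers dose changes and new drugs. Its motive concerns antidepressants in depressed patients, but its wording is not limited to them and contains no exception.

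2. **Scope of the assurance.** It is phrased as a fact about participants during the study. It names no procedure that makes it true.

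3. **Do the exclusions carry forward?** Criteria ii and iv describe who may enter. The stability rule looks back from enrollment. No sentence extends either to the treatment period or makes the permission subject to them.

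4. **Period left uncovered.** It runs from Session 1, the last listed safety screen, to the last stimulation session. Section 10.0 fits the three treatment days into at most eight days, but the text sets no maximum interval between Session 1 and Session 3.

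5. **What could catch a change in that period?**
   - The query at the start of each procedure (section 9.0) covers comfort and willingness.
   - Daily assessment during treatment (section 15.0) looks for worsening symptoms and suicidal thinking.
   - Weekly clinician contact takes place "during rTMS treatment and the one month study involvement to assess mood, functioning, and safety". It may be by telephone, is not tied to treatment days, and names no medication review.
   - Weekly quality control (section 13.0) covers participant status, adverse events and deviations.
   - Section 14.0 lists a generalized seizure as a ground for withdrawal, but not a newly started excluded drug. It also lets the PI withdraw someone in their best interest.
   - The adverse-events questionnaire is given on treatment days. Its items are not reproduced, so a medication item is possible, but no hold or decision is attached to one.

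6. **A worked case.** A participant passes the Session 1 screen. Before Session 3 their own physician starts theophylline, the protocol's own example of a seizure-risk drug. The paragraph on delaying treatment permits this; the seizure paragraph says it will not occur; the entry criteria were met when applied. No named treatment-day step asks. Whether stimulation goes ahead depends on the participant volunteering the information or on a questionnaire item that cannot be seen. The same sequence applies to bupropion, which criterion ii excludes by name.

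7. **Size.** The expected number exposed is 40 enrolled × the probability of starting such a drug in the period. The excess number of seizures would be that count × the increase in seizure probability due to the drug. The documents supply only the 40. The 20 seizures reported since 1997, cited in section 15.0, come without a denominator and yield no rate.

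**The case against.** The strongest reply is that the two paragraphs can be read together. The seizure paragraph is a specific safety limit and the medication paragraph a general statement of treatment as usual, so the specific should qualify the general. On that reading one linking clause cures a drafting ambiguity. The reading is reasonable, but neither paragraph says so, and staff who follow the permission as written are not told to apply it. Even if it is adopted, no named step enforces it.

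The second reply is that other safeguards exist: individualised intensity, observation for seizure signs, daily symptom checks, weekly contact that expressly includes safety, physicians on call, and open-ended PI discretion. These are real and lower the risk. None is triggered by a medication change, and observation and on-call response act mainly once a problem has appeared.

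The third reply is that some instruments and training materials cannot be seen. This stands. A reader might infer that the site never asks about medication before stimulating; the documents support only that the protocol states no such check. Nor is there a complete absence of a rule, since the assurance itself is one. The defect is that a stated permission contradicts it.

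**Conclusion.** The point holds as a conflict between two statements in section 15.0, with entry-only exclusions and no named treatment-day check to resolve it. It should be corrected, because it concerns the protocol's primary safety risk and the remedy is cheap. Confidence is medium, since the questionnaire items are not reproduced.

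The number affected cannot be estimated. A reader might take the 25-40% rate of comorbid depression in section 3.0 as a measure of exposure. It is not: it describes people with MCI in general and whom the medication paragraph has in mind, not how many would start a seizure-promoting drug between Session 1 and the last stimulation session. Nor do the documents support a claim that seizures are likely; section 15.0 calls them rare.

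The conflict does not depend on any one drug. The protocol does not say why bupropion is excluded. Treating it as a drug that lowers seizure threshold is an assumption for the physician co-investigators to confirm. Anticholinergics and sedatives are also in criterion ii, but the documents do not link them to seizure, so the point does not extend to them.

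A separate, minor mismatch concerns entry. Section 5.0 says "Stimulant use may be allowed pending investigator review", while the seizure paragraph says participants will be free of stimulants. No sample-size, power or analysis figure is affected by either issue.

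**What to change.** Amend the medication paragraph of section 15.0. Clinically needed changes remain allowed. If bupropion or another drug that lowers seizure threshold is started or changed before the last stimulation session, stimulation is held until the on-call physician (section 13.0) records proceed, hold or stop. Refer to this rule in the seizure paragraph so that the two agree.

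Add one question before the first stimulation session of each treatment day: has any medication been started, stopped or changed since you were last asked? A short reference list from the physician co-investigators would help staff recognise relevant drugs, but is optional. Section 13.0 already has the coordinator consult a physician before treating a participant who reports substance use, so this kind of hold is familiar; the routine question is new.

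Separately, align the stimulant wording in section 15.0 with the investigator review in section 5.0.

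The cost is a short amendment and at most 3 × 40 = 120 questions. The downside is an occasional delayed or stopped course. A hold that runs past the eight days could lead to withdrawal under section 14.0, item (d), so the amendment should say whether a held day may be made up later. Each stopped course also counts against retention as section 12.0 defines it: 1/40 = 2.5 percentage points, assuming the denominator is the 40 enrolled.
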